**Table 12: Axitinib Toxicity Management Guidelines (Continued)**

Event/Severity (CTCAE v5 Grade)	Management Guideline
Cardiac failure	
Asymptomatic cardiomyopathy (LVEF > 20% but < 50% below baseline or below the lower limit of normal of baseline was not obtained)	
 
Interrupt axitinib until resolution to Grade 0 or 1 or baseline.
 
Resume axitinib with a dose reduction of 1 level (see Table 9).
 

Clinically manifested CHF	Discontinue axitinib.
Fistula	
Trachea-esophageal fistula Any grade	Discontinue axitinib.
Fistula other than trachea-esophageal Grade 1 or Grade 2	
 
Interrupt axitinib.
 
Either resume axitinib at a dose reduction (see Table 9) or discontinue depending on the severity and persistence of the adverse reaction.
 

Fistula other than trachea-esophageal fistula Grade 3 or Grade 4	Discontinue axitinib.
Impaired wound healing	
Any grade	
 
The safety of resumption of axitinib after resolution of wound healing has not been established.
 
Either resume axitinib at a reduced dose (see Table 9) or discontinue, depending on the severity and persistence of the adverse reaction.
 

GI perforation	
Any grade	Discontinue axitinib.
Arterial thromboembolic events	
Any grade	Discontinue axitinib.
Venous thromboembolic events	
Any grade	
 
Interrupt axitinib.
 
Either resume axitinib at the same dose level or discontinue, depending on the severity of the VTE.
 
Permanently discontinue for severe VTE.
 

Hemorrhage	
Grade 1	
 
For hemoptysis, interrupt axitinib and evaluate underlying causes.
 
Resume axitinib at the discretion of the investigator.
 
For other Grade 1 hemorrhage/bleeding events, continue axitinib at the current dose level and monitor as clinically indicated.
 

**Table 12: Axitinib Toxicity Management Guidelines (Continued)**

Event/Severity (CTCAE v5 Grade)	Management Guideline
Hemorrhage (continued)	
Grade 2	
 
For pulmonary or GI bleed (other than hemorrhoidal bleeding): 
 
Discontinue axitinib.
 
 
 
Other bleeding events: 
 
Interrupt axitinib until the severity of the event improves to Grade <math>\leq 1</math>.
 
Resume axitinib with a dose reduction of 1 level (if permitted by Table 9).
 
 
 

Grade 3 and Grade 4	Discontinue axitinib.
Hypothyroidism	
All grades	Continue axitinib while thyroid replacement therapy is initiated. See Table 11 for further details on event management.
Hyperthyroidism	
Grade 1 and Grade 2	Continue axitinib at the current dose level. See Table 11 for further details on event management.
Grade 3	If symptoms can be controlled with symptomatic medications, or if asymptomatic: may continue axitinib at the same dose level or dose reduced by 1 dose level (see Table 9 ) per investigator judgment. See Table 11 for further details on event management.
Grade 4	
 
Hold axitinib until recovery to Grade <math>\leq 1</math> or baseline.
 
Resume axitinib at 1 dose level reduced (see Table 9).
 
 See Table 11 for further details on event management.
Reversible posterior leukoencephalopathy syndrome/posterior reversible encephalopathy syndrome	
Any grade	Discontinue axitinib.
Proteinuria	
Grade 1 1+ proteinuria OR Urinary protein $\geq$ ULN to $< 1$ g/24 h AND Without nephrotic syndrome	Continue axitinib at the current dose level.
Grade 2 and Grade 3 $\geq 2+$ proteinuria OR Urinary protein 1 to $< 3.5$ g/24 h AND Without nephrotic syndrome	Proteinuria $\geq 2+$ on dipstick urinalysis 
 
Perform 24-hour urine collection and measure total protein.
 
May continue with axitinib while awaiting results: 
 
<math>< 2</math> g protein/24 hour 
 
Continue axitinib at the current dose level.
 
 
 
<math>\geq 2</math> g protein/24 hour 
 
Interrupt axitinib until proteinuria <math>< 2</math> g/24 h.
 
Repeat 24-hour urine collection and protein measurement (frequency at discretion of the investigator) until proteinuria <math>< 2</math> g/24 h.
 
 
 
 
 
Resume axitinib at a reduced dose (see Table 9).
 

**Table 12: Axitinib Toxicity Management Guidelines (Continued)**

Event/Severity (CTCAE v5 Grade)	Management Guideline
Proteinuria (continued)	
Nephrotic syndrome	Discontinue axitinib.
Creatinine increased	
Grade 1 or Grade 2	Continue axitinib at the current dose level. See Table 11 for further details on event management.
Grade 3 or Grade 4	
 
Interrupt axitinib until recovery to Grade < 2
 
Resume axitinib with a dose reduction of 1 level (see Table 9)
 
 
Note: Caution should be used in participants with end-stage renal disease (CrCl < 15 mL/min). See Table 11 for further details on event management.

Other adverse reactions	
Grade 1, Grade 2	Continue axitinib at the current dose level.
Grade 3	Reduce axitinib by 1 dose level (see Table 9 ).
Grade 4	
 
Interrupt axitinib until resolution to Grade < 2.
 
Resume axitinib when severity has improved to Grade ≤ 2 with a dose reduction of 1 level (see Table 9).
 

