### 6.6.1. Dose Interruptions

The doses of INCB099280 and axitinib may be adjusted by dose interruptions with or without dose reductions of axitinib. Treatment interruptions for AEs associated with INCB099280 and axitinib are provided in [Table 11](#), [Table 12](#), [Table 13](#), and [Table 14](#). The criteria for dose interruptions are based on the severity of an AE. Treatment interruptions may occur independently for the 2 study drugs. Study treatment may also be interrupted for reasons other than treatment-related AEs (such as medical/surgical events or logistical reasons not related to study therapy).

In general, treatment may resume once the AE has improved to  $\leq$  Grade 1 unless there are other comorbidities or other circumstances present that would contraindicate the resumption of study treatment.

Treatment may be interrupted for up to 3 weeks (21 days), after which it should be discontinued. However, if further clinical benefit is anticipated with resumption of treatment, interruptions between 4 and 8 weeks may be considered in consultation/agreement with the sponsor.

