### 6.6.3. Criteria and Procedures for Dose Interruptions and Adjustments of Study Drug

Safety concerns should be discussed with the sponsor immediately upon occurrence or awareness to determine if the participant should continue or discontinue study treatment.

Treatment with INCB099280 and axitinib may be delayed up to 3 weeks (21 days) to allow for resolution of toxicity. Participants may resume treatment if no medical condition or other circumstance exists that, in the opinion of the investigator, would make the participant unsuitable for participation in the study. The treating investigator should contact the sponsor to discuss the case of a participant whose treatment has been delayed for more than 21 days before restarting treatment with INCB099280 or axitinib.

Management guidelines for AEs requiring dose modifications for INCB099280 and axitinib are described for general toxicities (see [Section 6.6.4](#)) and for irAEs (see [Section 6.6.5](#)). Participants requiring dose reduction of INCB099280 will be discontinued from INCB099280 treatment. Dose reductions of axitinib should be made following the dose-modification guidelines and

according to the clinical judgment of the investigator. Participants may resume treatment once the AE resolves to  $\leq$  Grade 1 or baseline if no medical condition or other circumstance exists that, in the opinion of the investigator, would make the participant unsuitable for further treatment and participation in the study.

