**Table 10: Non-Immune-Related Adverse Event Management Guidelines for INCB099280**

CTCAE Grade	Suggested Modification for INCB099280
Grade 1 or Grade 2	Continue treatment at the discretion of the investigator.
Grade 3	Withhold treatment until resolution to $\leq$ Grade 1 or baseline. Restart INCB099280 at the same dose at the discretion of the investigator. Permanently discontinue study drug at the third occurrence unless approved by the medical monitor to continue.
Grade 4	Permanently discontinue study treatment or discuss with the medical monitor if a treatment algorithm for CTCAE Grade 3 events (above) is appropriate.

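### Table 12's Grade 4 row for other adverse reactions gives two axitinib resumption thresholds that contradict each other at Grade 2

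*Protocol*

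**What the plan says.** Protocol Table 12 ends with a catch-all block for adverse reactions that have no row of their own. Its Grade 4 row has two bullets. The first reads "Interrupt axitinib until resolution to Grade", followed by < 2. The second reads "Resume axitinib when severity has improved to Grade ≤ 2 with a dose reduction of 1 level".

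Two general rules sit above the tables:

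- Section 6.6.1: "In general, treatment may resume once the AE has improved to" Grade 1 or lower. It adds that "Treatment interruptions may occur independently for the 2 study drugs".
- Section 6.6.3: "Participants may resume treatment once the AE resolves to" Grade 1 or lower, or baseline.

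Sections 6.6.1 and 6.6.7 limit an interruption to 21 days, after which treatment is to be discontinued unless the sponsor agrees to a longer hold.

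Table 10 covers non-immune events, with the action column headed "Suggested Modification for INCB099280". Its Grade 4 row says: "Permanently discontinue study treatment or discuss with the medical monitor if a treatment algorithm for CTCAE Grade 3 events (above) is appropriate". Section 6.6.3 points to the section that holds Table 10 for both drugs: "Management guidelines for AEs requiring dose modifications for INCB099280 and axitinib are described for general toxicities".

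**The concern.** The two bullets are meant to describe one sequence, hold and then resume, yet the hold ends at one grade and the restart begins at another. A site with a participant recovering at Grade 2 can keep axitinib on hold or restart it, and follows the printed text either way.

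Two things are at stake. The row governs re-exposure after a Grade 4 event, so sites could treat the same clinical state differently. In addition, the incidence of TEAEs leading to interruption, reduction or discontinuation of either drug is a primary endpoint in Part 1 and a secondary endpoint in Part 2 (Tables 1 and 4). Part of that endpoint could then reflect which bullet a site followed rather than how well the combination is tolerated.

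**Working it through.** No sample size, error rate or power figure is involved, so the check sets the passages side by side.

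**Step 1. Apply each rule to the current grade of an event that began at Grade 4 and falls in the catch-all row.**

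| Current grade | Table 12, bullet 1 (< 2) | Table 12, bullet 2 (≤ 2) | Sections 6.6.1 and 6.6.3 (≤ 1; 6.6.3 adds baseline) |
|---|---|---|---|
| 3 or 4 | hold | hold | hold |
| 2 | hold | resume, one level lower | hold, unless Grade 2 is the baseline (6.6.3) |
| 0 or 1 | resume | resume, one level lower | may resume |

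Below Grade 2 means Grade 0 or 1, which is the same as Grade 1 or lower. Bullet 1 therefore matches the general rule, and only bullet 2 departs from it. The contradiction is confined to participants whose event has improved to Grade 2.

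**Step 2. Look for a rule that settles it.** Section 6.6 tells sites to take the most conservative recommendation when attribution between the two drugs is hard, so it does not reach an event clearly attributed to axitinib. Section 6.6.1 is worded as a general rule, so bullet 2 could be read as a deliberate exception, but nothing says that it is one. The other grade-based axitinib resumption rules in Tables 12 and 13 (asymptomatic cardiomyopathy, Grade 2 hemorrhage, Grade 4 hyperthyroidism, creatinine, liver enzymes, Grade 4 diarrhea) all use Grade 0 or 1, some adding baseline. They show that bullet 2 stands alone; they do not show which threshold was intended.

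**Step 3. Trace the effect on what is recorded.** Assume that Table 9 still offers a lower axitinib level.

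- *Event reaches Grade 1 within 21 days of the hold.* Under either bullet the participant has an interruption followed by a one-level reduction. Only the restart date differs, and the endpoint categories are the same.
- *Event reaches Grade 2 within 21 days and is still at Grade 2 after day 21.* Under bullet 2 axitinib has already restarted one level lower: interruption plus reduction. Under bullet 1 the hold passes the 21-day limit and, without sponsor agreement to extend it, ends in discontinuation: interruption plus discontinuation.

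The second path is where the wording can change the endpoint category.

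**Step 4. Check the scope of Table 10.** Its title and only action column name INCB099280. Section 6.6.6.3 sends axitinib modifications to Tables 12 to 14, and the lists in Sections 6.6, 6.6.1 and 6.6.7 name Tables 11 to 14 without Table 10. Against that, its Grade 4 row says study treatment rather than INCB099280, and Section 6.6.3 refers both drugs to Section 6.6.4. The scope is ambiguous.

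**The case against.** The strongest defence is that both bullets can be obeyed at once: wait until the event is below Grade 2, and the second condition is then met automatically. That is true, but it makes the threshold in the second bullet redundant, and a site that restarts at Grade 2 has still followed the print.

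It can also be said that safeguards surround the row. Section 6.6.3 asks for safety concerns to be discussed with the sponsor at once, and Section 6.6 has both drugs interrupted when an event is severe or life-threatening at onset or worsens rapidly. These make an unexamined restart less likely. They do not supply a threshold.

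The endpoint argument is fairly limited by the fact that interruption length is not an endpoint. For most participants the categories recorded would be the same under either bullet. What remains is the 21-day path in Step 3, which the sponsor can close by approving a longer hold.

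A reader might infer that Table 10 contradicts Table 12 outright, so that the same event calls for permanent discontinuation of both drugs in one table and an axitinib restart in the other. The documents do not support that. Table 10 is headed for INCB099280, the two drugs may be interrupted separately, the cross-references for axitinib omit Table 10, and its Grade 4 row itself offers an alternative to permanent discontinuation. Only the scope question stands.

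**Conclusion.** The two bullets of the Table 12 row give opposite instructions at Grade 2, and no other passage resolves them. This rests on current text and needs no assumption. The second bullet also departs from Sections 6.6.1 and 6.6.3; the row as a whole does not, because the first bullet agrees with them.

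The size is one CTCAE grade in a re-exposure rule. The possible shift from dose-reduced to discontinued rests on three conditions: the event stays at Grade 2 beyond day 21, the sponsor does not extend the hold, and a lower axitinib level is still available.

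A reader might be tempted to give a headcount by applying an assumed Grade 4 rate to the planned 132 participants. The document gives no rate of Grade 4 events outside the named rows, and Tables 12 and 13 already take out many events, including hypertension, hemorrhage, thromboembolism, liver enzymes and diarrhea. The number cannot be estimated.

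Table 10 is a secondary matter of unclear scope, not a direct conflict with Table 12.

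**What to change.** - In the Table 12 Grade 4 row for other adverse reactions, reconcile the two bullets to one resumption threshold.
- Align that threshold with Sections 6.6.1 and 6.6.3, or state in the row that it is a deliberate exception to them.
- In the Table 10 Grade 4 row, state whether study treatment means INCB099280 only or both drugs, and make the Section 6.6.3 cross-reference agree.

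The choice of threshold belongs to the sponsor's clinical team; this review takes no view on it. The cost is a wording change at the next amendment, with no added procedures, visits or participants.

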**Table 13: Management Guidelines for Specific Adverse Events Common to Both INCB099280 and Axitinib**

Event/Severity (CTCAE v5 Grade)	Evaluation and Management
Liver enzyme elevationa	
ALT/AST ≥ 3 × ULN but < 10 × ULN without concurrent total bilirubin ≥ 2 × ULN	
 
Interrupt both INCB099280 and axitinib until resolution to Grade 0-1.
 
Consider rechallenge with INCB099280 and axitinib.
 
 
See Table 14 for further details on event management.

ALT/AST ≥ 3 × ULN with concurrent total bilirubin ≥ 2 × ULN or ALT/AST ≥ 10 × ULN	Permanently discontinue both INCB099280 and axitinib.
Diarrhea	
Grade 1 or Grade 2	Initiate symptomatic medications. See Table 11 for further details on event management.
Grade 3	
 
Interrupt axitinib and initiate symptomatic medications.
 
If diarrhea is controlled, axitinib may be resumed at either the same dose level or reduced by 1 dose level (see Table 9).
 
 
See Table 11 for further details on event management.

Grade 4	Interrupt axitinib until resolution to Grade < 2, then restart axitinib dose reduced by 1 dose level (see Table 9 ). See Table 11 for further details on event management.
Major adverse cardiovascular events	
Grade 3 and Grade 4	Permanently discontinue both INCB099280 and axitinib.

a Consider corticosteroid therapy.

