## Medications

31. Received systemic antibiotics within 14 days of the initiation of study treatment.

32. Probiotic usage during screening and throughout the study treatment period.

33. Treatment with systemic immunosuppressive medication, including (but not limited to) glucocorticoids with daily doses exceeding an equivalent of 10 mg of prednisone per day, within 14 days prior to the initiation of study treatment.

34. Treatment with vitamin K antagonists.

Note: Therapeutic use of the following agents is allowed:

- Low-molecular-weight heparin
- Direct-acting oral coagulants in alignment with each agent's posology (see Section 6.7.2.2).

35. Received a live-attenuated vaccine within 28 days of the planned start of study treatment or anticipated need to receive such a vaccine during the treatment period and up to 90 days after the last dose of study treatment has been administered.

- Examples of common live-attenuated vaccines include, but are not limited to, MMR, chickenpox/zoster, yellow fever, rabies, BCG, typhoid, and LAIV.

Note 1: Seasonal influenza vaccines for injection are generally killed virus vaccines and are allowed; however, intranasal influenza vaccines are live-attenuated vaccines and are not allowed.

Note 2: COVID-19 vaccines (eg, mRNA) are allowed as long as they are not live vaccines.

36. Treatment with moderate and potent [REDACTED] inhibitors or inducers or drugs that are known to have proarrhythmic potential (see [Appendix C](#)).

Note: A washout period  $\geq 10$  days before the first dose of INCB099280 is required for prior treatment with moderate or potent [REDACTED] inhibitors or inducers.

37. Unable to discontinue medication that is prohibited by this study (see Section [6.7.3](#)) before the initiation of study treatment.

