**Table 6: Exclusionary Laboratory Values (Continued)**

Laboratory Parameter		Exclusion Criterion
i	Urine protein	$\geq 2+$ by dipstick urinalysis and $\geq 2$ g urinary protein per 24 hours on a 24-hour urine collection or urine protein-to-creatinine ratio $\geq 2$
Coagulation		
j	INR	$> 1.5 \times$ institutional ULN (if not receiving therapeutic anticoagulation) $> 2 \times$ institutional ULN (if receiving therapeutic anticoagulation)
k	PT	$> 1.5 \times$ institutional ULN (if not receiving therapeutic anticoagulation) $> 2 \times$ institutional ULN (if receiving therapeutic anticoagulation)
l	aPTT	$> 1.5 \times$ institutional ULN
Bone profile		
m	Corrected serum calcium	$> 2.9$ mmol/L ( $> \text{Grade } 1$ ) despite maximal antihypercalcemic therapy

a Cockcroft and Gault (1976):  $\text{CrCl} = \{([140 - \text{age}] \times \text{weight [kg]}) / (72 \times \text{serum creatinine})\} \times 0.85$  (if female).

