  - Promptly interrupt (or permanently discontinue) both study drugs and any other suspected concomitant medications, including over-the-counter and herbal medications and supplements.
  - Adequately monitor liver enzymes and LFTs. This should include AST, ALT, alkaline phosphatase, total bilirubin, direct bilirubin, and PT/INR. Repeat LFTs within 24 to 72 hours to confirm the initial laboratory value. Continue to monitor LFTs at least twice weekly, while evaluating other causes, until AST/ALT values are trending downward.

While corticosteroid therapy is essential for managing immune-mediated hepatitis, administering immunosuppressants prior to identifying the most likely causes of transaminase elevation will confound the causality assessment and impact proper management of the event. Initiating corticosteroids should be considered if transaminase elevation:

- Is associated with clinical significant hepatic dysfunction (eg, AST/ALT  $> 3 \times$  ULN with concurrent total bilirubin  $\geq 2 \times$  ULN (excluding biliary obstruction) and/or PT/INR  $\geq 1.5 \times$  ULN
- OR
- Has been persistent or further increased (without an alternative cause identified); consider observing liver biochemistry for approximately 3 to 7 days prior to making the decision if the participant is stable.

Rechallenge after AST/ALT elevation:

- Rechallenge should occur at the discretion of the investigator in consultation with the medical monitor. The guidelines in [Table 14](#) are suggestions; clinical judgment should always be used when deciding whether or not to restart each study drug.

Recommended axitinib dose modifications in case of drug-related toxicity are shown in [Table 12](#), [Table 13](#), and [Table 14](#).

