**Table 14: Algorithms of Decision on INCB099280/Axitinib Rechallenge After Recovery From Drug-Related ALT/AST Elevation**

Initial ALT/AST Elevation Scenario	Rechallenge Decision
Scenario 1: ALT/AST $> 3 \times \text{ULN}$ concurrent with total bilirubin $\geq 2 \times \text{ULN}$ (excluding biliary obstruction) and/or PT/INR $> 1.5 \times \text{ULN}$ (ie, ALT/AST elevation with clinically significant signs of hepatic dysfunction)	No rechallenge with either INCB099280 or axitinib is allowed.
Scenario 2: ALT/AST $> 3\text{-}5 \times \text{ULN}$ without clinically significant signs of hepatic dysfunction (ie, total bilirubin $< 2 \times \text{ULN}$ and PT/INR $< 1.5 \times \text{ULN}$ )	
Unacceptable toxicity or the inability to tolerate study treatment with both INCB099280 and axitinib will require discontinuation from both study drugs.
 
Combination treatment with INCB099280 and axitinib can be resumed sequentially with axitinib (at the previous dose) resumed first for 2-3 weeks with weekly liver test monitoring:
 
 
• If no recurrence, rechallenge with INCB099280.
 
• If ALT/AST recurrence is <math>> 5 \times \text{ULN}</math> (ie, Grade 3 or 4), discontinue axitinib. A rechallenge with INCB099280 monotherapy may be considered on a case-by-case basis after discussion between the medical monitor and investigator. See Section 6.6.7 for further details.
 
• If ALT/AST recurrence is <math>> 3\text{-}5 \times \text{ULN}</math> (ie, Grade 2), reduce the dose of axitinib and then rechallenge or discontinue axitinib and rechallenge with INCB099280. If axitinib needs to be discontinued, on a case-by-case basis, after discussion between the medical monitor and investigator, INCB099280 monotherapy may be considered.
 
 
Permanently discontinue INCB099280 if ALT/AST recurrence is <math>> 5 \times \text{ULN}</math> or interrupt INCB099280 if ALT/AST recurrence is <math>> 3</math> to <math>5 \times \text{ULN}</math> after rechallenge.

Scenario 3: ALT/AST $> 5$ to $10 \times \text{ULN}$ without clinically significant signs of hepatic dysfunction (ie, total bilirubin $< 2 \times \text{ULN}$ and PT/INR $< 1.5 \times \text{ULN}$ ).	No rechallenge with either INCB099280 or axitinib is allowed.
Scenario 4: ALT/AST $> 10 \times \text{ULN}$ without clinically significant signs of hepatic dysfunction	No rechallenge with either INCB099280 or axitinib is allowed.

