Note 1: Participants should have weekly monitoring with liver tests (ie, liver enzyme and function tests) for 2-3 weeks after each drug rechallenge.

Note 2: If both study drugs are discontinued due to a hepatic event, participants should be monitored until AE resolution as per Protocol and continue imaging as per Protocol.

Note 3: Liver tests include liver enzyme (ALT, AST, and ALP) and liver function (bilirubin and PT/INR) tests.

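### Table 13 offers rechallenge after ALT/AST of >5 to <10 × ULN, where Table 14 bars it; separately, Section 6.8 conditionally allows warfarin, which exclusion 34 and Section 6.7.3 prohibit

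*Protocol*

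**What the plan says.** **Liver enzymes.** The first liver row of Table 13 covers ALT/AST of at least 3 and below 10 × ULN without total bilirubin of 2 × ULN or more. Both drugs are interrupted until Grade 0-1, and then: "Consider rechallenge with INCB099280 and axitinib". The cell refers to Table 14 for detail. The second row stops both drugs for good at 10 × ULN or above, or at 3 × ULN or above with bilirubin of at least 2 × ULN.

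Table 14 has four scenarios. Only Scenario 2 (>3 to 5 × ULN, "without clinically significant signs of hepatic dysfunction") allows a restart, in sequence with axitinib first. Scenario 3 (>5 to 10 × ULN, bilirubin below 2 × ULN and PT/INR below 1.5 × ULN) reads: "No rechallenge with either INCB099280 or axitinib is allowed". Scenarios 1 and 4 say the same.

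On the standing of Table 14, Section 6.6.6.3 says: "Rechallenge should occur at the discretion of the investigator in consultation with the medical monitor". It adds that the table's guidelines "are suggestions; clinical judgment should always be used when deciding whether or not to restart each study drug".

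**Warfarin.** Exclusion 34 reads "Treatment with vitamin K antagonists"; its note allows low-molecular-weight heparin and direct oral agents. Section 6.7.3 extends exclusionary drugs to the treatment period, requires study treatment to be interrupted or discontinued if one is clinically indicated, and lists vitamin K antagonists as prohibited without exception. Section 6.8 says that when low-dose heparin cannot be given, warfarin, other coumarins or other anticoagulants may be allowed, with PT/INR monitoring.

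**The concern.** A participant with ALT at 7 × ULN and normal bilirubin and INR meets both Table 13 row 1 and Table 14 Scenario 3. One invites a restart of both drugs after recovery; the other forbids a restart of either. Sections 6.6.6 and 6.6.6.3 say that liver enzyme rises are hard to attribute between these two drugs, so the restart rule should be unambiguous.

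Warfarin raises the same kind of problem. A participant who needs anticoagulation and cannot have heparin stays on study treatment under Section 6.8, but must have it held or stopped under Section 6.7.3. Section 6.6 names hemorrhage as a known axitinib risk.

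At stake are participant safety and consistent conduct across sites. A site that follows Table 13 or Section 6.8 as written breaks another rule of the same protocol.

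**Working it through.** The plan states no figure on this point, so the check compares text.

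**Step 1: Tables 13 and 14 by ALT/AST interval, with bilirubin <2 × ULN and PT/INR <1.5 × ULN**

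| ALT/AST (× ULN) | Table 13 | Table 14 | Agree? |
|---|---|---|---|
| >3 to 5 | Interrupt, consider rechallenge | Scenario 2: sequential rechallenge possible | Yes |
| >5 to <10 | Interrupt, consider rechallenge | Scenario 3: none | **No** |
| 10 | Permanent stop | Scenario 3: none | Yes |
| >10 | Permanent stop | Scenario 4: none | Yes |

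The conflict fills the whole band from >5 to <10 × ULN.

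**Step 2: PT/INR.** Scenario 1 also bars rechallenge at >3 × ULN when PT/INR exceeds 1.5 × ULN. Table 13 does not mention PT/INR. This is an omission that the reference to Table 14 largely fills. Once the band in Step 1 is corrected, it matters only at >3 to 5 × ULN with bilirubin below 2 × ULN.

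**Step 3: does other text decide the >5 to <10 × ULN band?**

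- Section 6.6: when attribution to one drug is difficult, the most conservative recommendation applies. That selects Table 14, but does not reach a clearly attributed event.
- Table 11: Grade 3 immune-related hepatitis ends INCB099280 permanently, and Table 14 equates >5 × ULN with Grade 3 or 4. This agrees with Scenario 3 for immune-related events, but concerns INCB099280 only.
- Section 6.6.7: study treatment must end when a discontinuation criterion in Tables 11 to 14 is met. Scenario 3 naturally reads as such a criterion, although it is worded as a bar on rechallenge.
- Section 6.6.6.3: the Table 14 guidelines are suggestions, subject to judgment. This points the other way.

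Take a rise to 7 × ULN that resolves promptly on stopping axitinib, without steroids; Section 6.6.6.3 would attribute it to axitinib. The Section 6.6 tie-break and Table 11 are then not engaged. What remains is Scenario 3, read with Section 6.6.7, against Table 13, read with Section 6.6.6.3.

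**Step 4: warfarin**

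| Provision | Vitamin K antagonist during treatment |
|---|---|
| Exclusion 34, carried over by Section 6.7.3 | Not allowed; hold or stop study treatment if indicated |
| Section 6.7.3 list | Prohibited, no exception |
| Section 6.7.1 | Clinically indicated treatment is allowed except what Section 6.7.3 prohibits |
| Section 6.8 | May be allowed if low-dose heparin cannot be given |

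Three provisions point to prohibition and one to conditional use. They cannot all be followed.

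**Step 5: frequency.** The protocol gives no ALT/AST distribution by ULN multiple for this combination and no rate of warfarin use. For orientation only, Section 2.3.2 reports Grade 3 or 4 ALT increase in 13.3% of participants on axitinib plus pembrolizumab. If that rate held here, which is an assumption, 0.133 × 132 = 17.6, or about 18 participants at full enrollment. The conflict band would be an unknown part of these, anywhere from 0 to about 18 on ALT alone, because the figure includes events at 10 × ULN or above and events with hepatic dysfunction.

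**The case against.** The strongest reply is that the protocol already settles the liver question. Table 13 only says to consider rechallenge and sends the reader to the dedicated algorithm, which says no. Section 6.6, Table 11 and Section 6.6.7 all lean the same way. Much of this stands: Table 13 is the outlier, and a site that follows the reference reaches the stricter rule. A reader might infer that the protocol leaves the matter wholly open, and the documents do not support that. What remains is narrower. A detail that forbids what its own summary row offers is still a contradiction, and Section 6.6.6.3 weakens the stricter text, most clearly for events attributed to one drug.

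The safeguards are also real: both drugs are interrupted first, the medical monitor is consulted, and Note 1 to Table 14 says "Participants should have weekly monitoring with liver tests" for 2 to 3 weeks after each rechallenge. They lower the risk but do not reconcile the instructions.

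On warfarin, a reader might infer that Section 6.8 permits it freely. It does not: the allowance depends on heparin being unusable and is worded as a possibility. Section 6.7.1 supports the prohibition as the governing rule. The conditional allowance still conflicts with a prohibition that has no exception.

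The missing PT/INR criterion might be read as a further contradiction. It is an incomplete summary, since Scenario 1 supplies the criterion.

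**Conclusion.** Both inconsistencies are in the current text and should be corrected. The liver defect is an over-broad summary row in Table 13. It conflicts with Table 14 Scenario 3 across >5 to <10 × ULN, with most other text favouring Scenario 3 and Section 6.6.6.3 leaving room to depart from it. The warfarin defect is the plainer contradiction, though it is limited to participants who cannot receive low-dose heparin.

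The size is the scope of the conflicting instructions; the protocol does not allow a count of affected participants. A reader might infer that the inconsistency threatens the response results. Nothing in the documents supports an effect on ORR, DOR or sample size. The conclusion rests only on the wording of the current sections and on no assumed rate.

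**What to change.** **Table 13.** Limit the rechallenge row to ALT/AST of 3 to 5 × ULN without hepatic dysfunction as defined in Table 14 Scenario 2. Extend the permanent-discontinuation row to >5 × ULN, or >3 × ULN with hepatic dysfunction as defined in Scenario 1. Both changes are needed: narrowing the first row alone would leave a participant at 3 to 5 × ULN with PT/INR above 1.5 × ULN and bilirubin below 2 × ULN in neither row. If the sponsor does intend rechallenge at >5 to 10 × ULN, amend Scenario 3 instead.

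Three edges need a decision at the same time so that no case falls between rows:

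- PT/INR of exactly 1.5 × ULN is in neither Scenario 1 (above) nor Scenario 2 (below).
- Scenario 1 leaves out biliary obstruction, so Table 13's existing bilirubin trigger should be kept.
- Table 6 admits participants on therapeutic anticoagulation with INR or PT up to 2 × ULN. The clinical team should say how PT/INR raised by permitted anticoagulation counts as hepatic dysfunction.

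**Section 6.8.** Delete the allowance for warfarin and other coumarins, and keep the alternatives that the note to exclusion 34 permits.

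**Cost.** Amendment wording in Table 13 (or Scenario 3) and Section 6.8, plus a letter to sites. Design, sample size and analyses are unchanged.
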